5.5.2. Sensitivity analyses

Not Applicable.

5.5.3. Supplementary analyses

Intra-reader variability at patient level

Intra-reader variability will be analyzed in a subgroup of 10% of patients randomly selected for whom the independent readers have re-read the images.

For the primary evaluation criterion, intra-reader variability will be studied using the Cohen kappa (κ) statistics. Agreement will be classified according to the value of the Cohen kappa statistics as described in the table below:

Table 4: Agreement according to Cohen kappa (κ) statistics

Cohen kappa statistics	Agreement
< 0.2	Poor agreement
$\geq 0.2 - \leq 0.4$	Fair agreement
$> 0.4 - \leq 0.6$	Moderate agreement
$> 0.6 - \leq 0.8$	Good agreement
$> 0.8 - 1.0$	Very good agreement

Inter-reader variability at patient level

Inter-reader variability will be evaluated on the whole set of trial patients, since each case will be read by the two independent readers.

The same methodology as the one presented above for intra-reader variability will be applied.

Diagnostic quality of CBV map assessed by on-site readers

The same methodology and analyses as the ones presented for the primary criterion will be applied to diagnostic quality of the CBV map according to the on-site readers.

CONFIDENTIAL	STATISTICAL ANALYSIS PLAN N° GDX-44-016 VERSION N° 4.0 (REF I011622)	F015830-03 Page 25 / 35
--------------	--	----------------------------

If the primary endpoint concluded to the non-inferiority of Elucirem versus Dotarem (off-site readers), then the non-inferiority will be tested for on-site readers: If the lower bound of the two-sided 95% CI is above the pre-stated margin of non-inferiority (-12%), Elucirem® will be declared non-inferior to Dotarem®.

In case of conclusion of non-inferiority of Elucirem® compared to Dotarem®, the superiority of Elucirem® compared to Dotarem® will then be tested in the same way as described above for the non-inferiority. No adjustment for multiplicity is needed as it is a simple closed testing procedure.

This secondary analysis will be performed on the On-site PPS and then on the On-site FAS and presented by arm only on one hand, and by arm and grade assigned at randomization on the other hand.

Quantification of the relative CBV for differentiating tumor grade (off-site assessment)

The Mann-Whitney U-test will be used to test the difference in rCBV between the two trial arms by tumor grade categorization (low and high grade) and between patients with high-grade and low-grade gliomas, within each of the two study arms at the significant level of 5%. The analysis will be performed for off-site assessment and presented for each off-site reader and overall (taking into account the consensus decision).

If more than one lesion were detected by a reader, the maximum value for rCBV will be considered for the analysis at reader level. For the overall rCBV analysis taking into account the consensus decision, the maximum value for rCBV of consensus reading will be considered. If no consensus was needed, the maximum value for rCBV between the two off-site readers will be considered.

Two analyses will be performed. The first one will consider the gliomas' grade categorization (high-grade versus low-grade) according to the stratification factor used at randomization, the second one will use the tumor grade categorization as per histopathological results (if any) collected during the study.

Categorization as per histopathological results will be the following:

- Grade 1 and Grade 2 = Low grade,
- Grade 3 and Grade 4 = High grade.

The Benjamini-Hochberg method will be used to account for multiple testing for the two analyses separately.

Grade per categorization (high-grade versus low-grade) according to the stratification factor used at randomization will be cross tabulated with the categorization of the grade as per off-site reader assessment, by treatment arm.

If more than one lesion were detected by a reader, the worst grade according to rCBV will be considered. Then, for the overall analysis of grade according to rCBV taking into account the consensus decision, the worst grade according to rCBV of consensus reading will be considered. If no consensus was needed, the worst grade according to rCBV between the two off-site readers will be considered. Moreover, for patients with histopathological results, categorization of the grade per histopathology will be cross tabulated with the categorization of the grade as per off-site reader assessment, by treatment arm.

Categorization as per off-site reader assessment will be the following (according to the Imaging Charter V1.0):

- $rCBV < 1.75$ = Low grade,
- $rCBV \geq 1.75$ = High grade.

Assessment and evaluation of the T2* signal intensity time curve at lesion level (on-site and off-site assessment)

T2* signal intensity time curve will be visually assessed by on-site and off-site readers for the reliability of the curve in providing sufficient information for diagnosis purpose.

For on-site assessment, the number and percentage of lesions for whom the reliability of the curve provides suffice information will be tabulated by trial arms.

For the off-site assessment, the number and percentage of lesions for whom the reliability of the curve provides suffice information will be tabulated by trial arms.

CONFIDENTIAL	STATISTICAL ANALYSIS PLAN N° GDX-44-016 VERSION N° 4.0 (REF I011622)	F015830-03 Page 26 / 35
--------------	--	----------------------------

For lesions for whom the reliability of the curve provides suffice information, confidence in diagnosis will be presented, for each arm, by on-site readers and for the off-site assessment for each off-site reader, using a 5-point scale:

- 1 = nil: very uncertain,
- 2 = poor: uncertain,
- 3 = moderate: moderately certain,
- 4 = high: good certainty,
- 5 = excellent: very certain.

Confidence in diagnosis will be summarized qualitatively and quantitatively by trial arm. The on-site and off-site read outcomes will be separately analyzed.

For the overall reliability of the T2* signal intensity time curve taking into account the consensus decision, the worst confidence in diagnosis between the two readers will be considered if no consensus decision was needed (worst case scenario).

Assessment and evaluation of the T2* signal intensity time curve (off-site assessment)

Only for off-site readers, FWHM and the maximum signal drop will be tabulated at lesion level by off-site reader and compared between the trial arms using a Mann-Whitney U-test.

For the overall FWHM taking into account the consensus decision, the mean of values between the two readers for each lesion will be considered if no consensus decision was needed.

For the overall maximum signal drop taking into account the consensus decision, the maximum of values between the two readers for each lesion will be considered if no consensus decision was needed.

If the curve is not reliable, no calculation of FWHM and the maximum signal drop will be performed.

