Some studies with other GBCA have shown that reduced-contrast-dose (0.05 mmol/kg) DSC perfusion of the brain is comparable with those of the full-dose protocol in terms of diagnostic quality of perfusion CBV maps [16; 17]. In addition, no significant difference in CBV mean value was found.

Elucirem® (gadopiclenol) is a new chemical entity discovered and developed by Guerbet. It is a non-ionic macrocyclic gadolinium complex, of high kinetic stability, intended to be used in human, by intravenous administration, as a contrast agent for MRI with variable indications. Its safety and efficacy when used at the dose of 0.05 mmol/kg body weight (BW) in adults and in children of 2 years and older have been proven through the global clinical development program of gadopiclenol.

The present clinical trial aims to study the performance of Elucirem® at 0.05 mmol/kg in DSC-MRI perfusion of brain gliomas and to demonstrate that it is as efficient as Dotarem® at 0.1 mmol/kg for qualitative and quantitative CBV perfusion evaluation.

| | | |
|--|--|----------------------------|
|  CONFIDENTIAL | Protocol No. GDX-44-016 Version No. 1.0 - ITA Date 15 March 2023 | F015919-05 Page 20 / 59 |
|--|--|----------------------------|

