1.1.2. Secondary Objectives

- To evaluate the diagnostic quality of CBV perfusion map for Elucirem® and Dotarem® (on-site assessment)
- To compare the performance of DSC-MRI perfusion using Elucirem® at 0.05 mmol/kg to DSC-MRI using Dotarem® at 0.1 mmol/kg in differentiating glioma grade through the quantification of the relative CBV (rCBV, off-site assessment)
- To assess the reliability of the T2* signal intensity time curve in terms of confidence in diagnosis in DSC-MRI perfusion using Elucirem® at 0.05 mmol/kg (on-site and off-site assessments)
- To expand the previously established safety profile of Elucirem® at 0.05 mmol/kg in terms of incidence of adverse events (AEs).

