3. STATISTICAL METHODS

3.1. General considerations

After the database lock, the statistical analysis will be performed by a CRO Biostatistician on the basis of the present document.

A quality control of the statistical analysis will be performed to ensure the reliability of the results.

Thorough description of all parameters reported will be presented separately by arm. Summary tabulated results will be provided by arm and assessment time, if relevant, or they will be replaced by the corresponding individual data listings if too few subjects are concerned.

Tabulations of quantitative parameters will include the following summary statistics: Number of Patients / Mean / Standard Deviation (SD) / Minimum / Median / Maximum. The mean and median will be reported to 1 decimal more than the data; SD to 2 more decimals than the data; and minimum and maximum to the same number of decimals as the data.

Rules for rounding decimals (example= the weight):

If decimal is <0.5 then round the number down (example: 65.3kg is rounded to 65kg)

If decimal is ≥ 0.5 then round the number up (example: 65.6kg is rounded to 66kg)

Tabulations of frequencies for categorical data will include all possible categories and will display the number of observations in a category as well as the percentage (%) relative to the respective arm. Percentages will be rounded to one decimal place.

The baseline value will be defined as the last available value prior to administration of the investigational product.

All statistical tests will be performed at the significant threshold of 2.5% one sided (5% two-sided).

SAS® Version 9.4 (or later version) will be used for all descriptive summaries and inferential analyses.

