3.8. Multiple comparisons/Multiplicity

Multiple testing regarding secondary criteria (quantification of rCBV) will be taken into account by using the Benjamini-Hochberg method.

The adjusted p-values according to the Benjamini-Hochberg procedure will be calculated as follows:

$$p \text{ Benjamini-Hochberg} = \min (p \times nbp / j, 1)$$

where:

- p is the original p-value (without adjustment),
- nbp is the number of calculated p-values (i.e., the number of comparisons),
- j is the rank of the original p-value when all p-values are ranked in ascending order.

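### The rationale aims to show Elucirem as good as Dotarem for quantitative CBV, but the between-arm rCBV comparison has no effect estimate, confidence interval or grade-combined analysis

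*SAP*

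**What the plan says.** Protocol 1.1 (Trial Rationale) gives the trial's aim for Elucirem as "to demonstrate that it is as efficient as Dotarem® at 0.1 mmol/kg for qualitative and quantitative CBV perfusion evaluation". The same section supports half-dose imaging from earlier work with other agents: "In addition, no significant difference in CBV mean value was found".

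The formal secondary objective (Protocol 2.2, SAP 1.1.2) is narrower. It is to compare the two agents' performance in differentiating glioma grade through rCBV, and it has no equivalence or non-inferiority wording.

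The rCBV analysis is in Protocol 11.3.6.2 and SAP 5.5.3:

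- Between arms, within each grade: "The Mann-Whitney U-test will be used to test the difference in rCBV between the two trial arms by tumor grade categorization". The results go to Tables 14.2.2.15 and 17 (grade as stratified) and 19 and 21 (grade by histopathology).
- Within each arm: a Mann-Whitney test of high against low grade.
- Multiplicity: "The Benjamini-Hochberg method will be used to account for multiple testing for the two analyses separately".
- In the SAP, cross-tabulations by arm of rCBV-based grade (cut-off 1.75) against stratification grade and against histopathology (Tables 14.2.2.23 to 26).

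SAP 3.1 limits summaries of quantitative variables to n, mean, SD, minimum, median and maximum. Where SAP 5.5.3 speaks of an overall rCBV result, it means the result after reader consensus, not a result combined over grades.

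**The concern.** The two halves of the aim are treated differently. Diagnostic quality of the CBV map has a hypothesis, a margin of -12 points and a confidence-interval rule. rCBV has a test of difference, split by grade, and descriptive summaries. Failing to find a difference does not show that two agents agree. Without an interval, the reader cannot tell how large a shift the data leave open.

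The size of a shift matters here because the SAP applies one fixed cut-off, rCBV 1.75, to both arms. A systematic difference in rCBV level between agents would move patients across that cut-off in one arm and not the other.

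**Working it through.** **The plan's own figure.** With 94% in both arms, margin 0.12, one-sided 2.5% and 80% power:

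n = (1.96 + 0.8416)² × 2 × 0.94 × 0.06 / 0.12² = 7.849 × 0.1128 / 0.0144 = 61.5, so 62 per arm. Then 124 / 0.90 = 137.8, so 138 enrolled.

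Both figures reproduce. They concern map quality. Neither document gives power, SD or an expected grade split for rCBV.

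**Assumptions for the illustration (not in the documents).** True Elucirem-Dotarem shift of 0.5 SD in both grades, normal rCBV within grade, and 62 evaluable per arm split between low and high grade as shown. The test is two-sided at 5%, as in SAP 3.1.

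**Chance of missing the shift in one grade.** For normal data the Mann-Whitney test has efficiency 3/π = 0.955 relative to the t-test, so with n per arm in that grade

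miss = 1 − Φ(0.5 × √(0.955 n / 2) − 1.96).

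At n = 31: 0.5 × √14.80 = 1.924; 1.924 − 1.96 = −0.036; miss = 51%.

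| Split per arm | Miss, smaller grade | Miss, larger grade | Both (product) |
|---|---|---|---|
| 31 / 31 | 51% | 51% | 26% |
| 25 / 37 | 59% | 44% | 26% |
| 19 / 43 | 68% | 38% | 26% |
| 12 / 50 | 78% | 31% | 24% |

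Simulating the test itself gives slightly higher figures, with runs agreeing to within a point or two:

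- Even split: about 52-53% missed in each grade.
- Uneven splits: about 62-80% missed in the smaller grade and 31-45% in the larger.
- Missed in both grades: about 25-28%, or 30-33% after Benjamini-Hochberg if the family is the four tests of one analysis. The SAP does not list the family.

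**Sensitivity.** With right-skewed (lognormal) data and the same shift in raw SD, power at an even split is about 65%, so 35% missed. In a histology subset of 10-15 per arm per grade (assumed), unadjusted power is 16-24%.

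**Sample needed.** For 80% power at 0.5 SD within one grade: 2 × (2.8016 / 0.5)² = 62.8, so 63 per arm. Dividing by 0.955 gives 66 for Mann-Whitney. An even split provides 31.

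**What an interval would show.** The approximate 95% CI half-width of a Hodges-Lehmann shift is 1.96 × √((2/n) × π/3), in SD units:

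- n = 31 (one grade, even split): 1.96 × √0.0676 = 0.51 SD.
- n = 62 (grades combined by stratification, common shift): 1.96 × √0.0338 = 0.36 SD.

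Combining the grades raises power for a common 0.5-SD shift to about 78%. The stratified test still misses it in 22-24% of trials, so the main gain is the interval.

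**The case against.** The strongest reply is that no equivalence conclusion for rCBV is planned. The formal objective says only to compare. The phrase about quantitative evaluation stands in background rationale, and the remark about no significant difference describes earlier literature. Where the sponsor wants a non-inferiority claim it states a margin and an interval. This stands. A reader might infer from Protocol 1.1 that p > 0.05 will be reported as equivalence, but neither document says so, and it would be wrong to say that the plan draws an unsupported conclusion.

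Second, the between-arm test is not the only output that bears on the question. The within-arm tests and the cross-tabulations at 1.75 also do, and the latter show by arm how patients of each grade fall around the cut-off. This also stands, but none of these outputs carries an interval for a difference between arms, so the gap remains.

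Third, a reader might say that a half-SD shift would usually be missed in a given grade. The figures do not support that in general. It is close to an even chance at an equal split. In the larger grade of an unequal split the shift is found more often than not, and a shift present in both grades is flagged in at least one of them in roughly 72-75% of trials before adjustment.

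Fourth, the Benjamini-Hochberg adjustment ("Multiple testing regarding secondary criteria (quantification of rCBV) will be taken into account by using the Benjamini-Hochberg method") might look like a serious distortion, because it raises p-values where non-rejection is the welcome result. Its effect is small. The chance of missing in both grades rises by about 5 points. The high-versus-low p-values are likely to be small, and ranking the between-arm p-values with them softens the adjustment compared with applying it to the two between-arm tests alone.

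Finally, analysis by grade follows from the objective and the stratified randomisation. It is reasonable to keep it and add to it.

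**Conclusion.** The concern holds as a gap between aim and analysis. Protocol 1.1 aims to demonstrate comparable quantitative CBV performance, and the plan contains no between-arm rCBV estimate, no interval and no grade-combined comparison that could support it. A non-significant result could not fill that gap.

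The size depends on a 0.5-SD shift, normality and a grade split that the documents do not give. On those assumptions the planned tests miss such a shift in about a quarter of trials in both grades together, and in about half in each grade at an even split. With skewed data the miss rate can be lower.

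The primary non-inferiority analysis is unaffected.

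**What to change.** In SAP 5.5.3 and Tables 14.2.2.15, 17, 19 and 21:

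1. Report the Elucirem-Dotarem Hodges-Lehmann shift in rCBV, or the ratio of geometric means, with an unadjusted 95% CI within each grade.
2. Add one overall estimate with 95% CI, stratified by the randomisation grade. An aligned-rank or stratified Hodges-Lehmann estimate would do, as would a model of log rCBV with arm and grade as factors. A van Elteren test may accompany it, but it is a test and does not itself supply the estimate.
3. State that a non-significant between-arm test will not be taken as equivalence of rCBV, and that any quantitative statement will rest on the interval. Alternatively, confine the as-efficient claim of Protocol 1.1 to the qualitative endpoint.

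Taking the between-arm p-values out of the Benjamini-Hochberg family is optional and changes little.

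The cost is some SAP wording and a few columns in existing tables, with no new patients or data. The drawback is that the interval may be wide (about 0.36 SD either side overall and 0.51 SD within a grade of 31 per arm, on the assumptions above), which would weaken the quantitative claim.

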4.1 Inclusion Criteria

To be included in the trial, the patient must meet all these inclusion criteria.

1. Female or male adult patient (patient having reached legal majority age).

| | | |
|--|--|----------------------------|
|  CONFIDENTIAL | Protocol No. GDX-44-016 Version No. 1.0 - ITA Date 15 March 2023 | F015919-05 Page 23 / 59 |
|--|--|----------------------------|

2. Patient with naive or recurrent primary glial tumor detected at a previous CT or MR imaging, and scheduled for a follow-up contrast-enhanced MRI. Tumor grade (confirmed or highly suspected) should be available in patients' medical records.
3. Patient or, if the patient is unable to provide informed consent, the patient's legally acceptable representative, having read the information and having provided patient's consent to participate in writing by dating and signing the informed consent prior to any trial related procedure being conducted.
4. Patient affiliated to national health insurance according to local regulatory requirements.

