- IWRS connection will be done to randomize the patient and to obtain the IMPs box number.

Unenhanced and contrast-enhanced MRI examinations:

- Unenhanced and contrast-enhanced MRI will be performed according to the required sequences specified in [section 8.2.2](#)).
- IMP (Elucirem® or Dotarem®) will be injected intravenously (IV) at the appropriate dose using a power injector with a flow rate of minimum 4 mL/second. This will be followed by a saline flush of a 20 mL bolus of 0.9% saline delivered at the same flow rate. Preload bolus is allowed. If applied, the total dose (preload bolus + main bolus) of IMP (Elucirem® or Dotarem®) should not exceed 0.05 mmol/kg or 0.1 mmol/kg, respectively.
- The following information will be documented in the source document and recorded in eCRF
- : date and time of contrast agent injection, actual volume administered (documentation of difference from theoretical volume), actual injection rate, overdose (if any), number of vials dispensed, IMP box number(s), injection of saline flush (yes/no, volume), preload bolus (yes/no, volume).

8.1.3 ***Safety Visit – Visit 3 – 1 day post visit 2***

The safety visit (V3) will be performed by phone. During this visit, the following assessments or tasks will be performed:

- Use/change of concomitant treatments / procedures / therapeutic measures will be documented;
- Assessment of AEs will be documented.

8.1.4 ***Record of histopathology results – Within 30 days of V2***

For patients undergoing biopsy or surgery within 30 days of visit 2, the result of histopathology will be recorded. The date and type of exam (surgery, biopsy) as well as the tumor grade diagnosis are to be recorded.

| | | |
|--|--|----------------------------|
|  CONFIDENTIAL | Protocol No. GDX-44-016 Version No. 1.0 - ITA Date 15 March 2023 | F015919-05 Page 33 / 59 |
|--|--|----------------------------|

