8.4 Off-Site Reading of Images

Off-site image evaluations are image evaluations performed at sites that have not otherwise been involved in the conduct of the trial and by readers who have not had contact with patients, investigators, or other individuals involved in the trial.

Images will be evaluated by prospective evaluation of the blinded images in a centralized manner. All images will be sent to an imaging core laboratory (ICL), which will prepare the images for evaluation. The file headers of all the images transmitted in DICOM format are to be edited to remove patient or site identification. For all images, any sequence information will be removed. Scalar information in the MR images will be preserved. A complete audit trail of any changes to the file headers will be maintained.

| | | |
|--|--|----------------------------|
|  CONFIDENTIAL | Protocol No. GDX-44-016 Version No. 1.0 - ITA Date 15 March 2023 | F015919-05 Page 34 / 59 |
|--|--|----------------------------|

The blinded image evaluations will be performed by 2 independent blinded readers experienced in brain tumor and perfusion imaging. In case of discordance, a consensus meeting will be organised in order to reach an agreement. The following criterion will be concerned by the consensus in case of discordance:

- The localization of the lesion
- The diagnostic quality of the CBV map (primary criterion).
- rCBV quantification (consensus in the glioma grade, not in the rCBV value)
- Visual evaluation of the T2* signal intensity time curve, including the confidence in the diagnosis.

An imaging eCRF will be used to ensure that the images and the diagnostic findings are properly aligned and to ensure that all data necessary for the trial purpose are documented by the independent blinded readers.

8.4.1 *Manuals and Supplies*

Guerbet (or the ICL) will document the imaging tasks and obligations of the investigational site in an Imaging Manual. As defined in [section 8.2](#), the standardized image acquisition guidelines or imaging protocol will be provided to the sites as part of the Imaging Manual.

In addition, the Imaging Manual will detail the steps required for masking confidential patient information and transferring images to the ICL (if applicable).

Guerbet (or the ICL) will document the central imaging process in a Blinded Imaging Evaluation Charter.

8.4.2 *Site Qualification*

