1.2. Study design

The trial is designed as a prospective, multi-center, randomized, controlled and parallel arm comparison.

Once informed consent form (ICF) signed, the patients will perform a screening visit (V1) to confirm trial eligibility. The eligible patients will be randomized by Interactive Web Response System (IWRS) to determine the Investigational Medicinal Product (IMP) to be injected. They will undergo a DSC-MRI perfusion using Elucirem® or Dotarem® (MRI visit - V2).

A safety visit (V3) will be performed 1 day after the MRI visit by phone. Confirmation of tumor grade diagnosis, if available, will be collected up to 30 days after visit 2.

The randomization scheme will allocate patients in a 1:1 ratio to the two parallel arms. Stratification by glioma grades (low grades versus high grades) between the two arms will be managed by IWRS based on the diagnosis collected at screening.

Images will be evaluated by both on-site and off-site readers.

For on-site reads, at least one experienced neuroradiologist will be appointed in each investigational site at the start of the trial to read perfusion images of patients included at the site.

For off-site reads, all images will be sent to an Imaging Core Laboratory (ICL) which will prepare the images for evaluation. The off-site images evaluation will be performed by two Independent Blinded Readers (IBR) experienced in perfusion MRI and brain tumors. In case of discordance (for number of lesions detected, localization of the lesion(s), diagnostic quality of the CBV map (primary criterion), rCBV quantification (only the glioma grade, not the rCBV value) and/or visual evaluation of the T2* signal intensity time curve, including the confidence in the diagnosis), a consensus meeting will be organised in order to reach an

agreement. Matching of the lesion(s) assessed by the IBR, with the histopathological data provided by the site, if any, will be performed by a third reader (see Imaging Charter V1.0).

[figure not shown]
For this study, only off-site readers will be blinded to the nature of the Investigational Medicinal Product (IMP) injected.

The diagnosis obtained from previous (qualifying) imaging examinations will be considered as medical history to assess inclusion criteria. All the trial analyses will be only based on the images obtained through the trial MRI.

During the trial, the safety of the patients will be monitored and assessed based on the reporting of AEs.

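### Comparing the arms in grading glioma by rCBV is a secondary objective, but no between-arm difference in discrimination with a confidence interval is planned

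*SAP*

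**What the plan says.** SAP 1.1.2 and Protocol 2.2 set the objective of comparing the two agents "in differentiating glioma grade through the quantification of the relative CBV (rCBV, off-site assessment"). The target is discrimination between grades, and the comparison is between arms.

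SAP 5.5.3 (and, for the tests, Protocol 11.3.6.2) plans three things:

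- a Mann-Whitney test of rCBV "between patients with high-grade and low-grade gliomas, within each of the two study arms at the significant level of 5"%;
- Mann-Whitney tests of rCBV level between arms, separately in low and in high grade;
- in the SAP only, tables in which the stratification grade "will be cross tabulated with the categorization of the grade as per off-site reader assessment, by treatment arm", and likewise the histopathology grade where there is one. The reader grade is low below an rCBV of 1.75 and high from 1.75 upwards.

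The tests are run once with stratification grade and once with histopathology grade, with BH adjustment applied to each analysis separately. The corresponding outputs are Tables 14.2.2.15 to 14.2.2.26. Neither the text nor the table titles name an AUC, sensitivity, specificity, a between-arm difference in any of these, or an interval.

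For the overall read, SAP 5.5.3 says that "the maximum value for rCBV of consensus reading will be considered". SAP 1.2 describes the discordance that leads to consensus as "rCBV quantification (only the glioma grade, not the rCBV value"), and Protocol 8.4 says "rCBV quantification (consensus in the glioma grade, not in the rCBV value").

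On the reference grade, Protocol 4.1 states that "Tumor grade (confirmed or highly suspected) should be available". Protocol 8.1.4 limits the histology: "For patients undergoing biopsy or surgery within 30 days of visit 2, the result of histopathology will be recorded".

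**The concern.** The planned tests answer neighbouring questions. The within-arm tests ask whether each agent separates the grades at all. One arm significant and the other not is not evidence that the arms differ, and both significant is not evidence that they are alike. The between-arm tests ask whether rCBV runs higher with one agent inside a grade. A uniform shift does that while leaving the AUC unchanged. The level tests are still relevant, because such a shift moves sensitivity and specificity at a fixed cut-off, but significance alone does not say which of the two has happened. The cross-tabulations come closest, yet they carry no statement of precision.

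At stake is the wording of a secondary conclusion. Without an interval, two significant p-values or a non-significant level test could be reported as equivalent grading, and a split result as a difference.

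Three definitions feed the same analysis and leave the programmer to choose:

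- **Overall value.** The overall rCBV is tied to a consensus reading, while consensus covers the grade and not the value.
- **Lesion used.** Protocol 8.4.10 sets up lesion matching to histopathology for the rCBV evaluation, and the histology tables are restricted to patients with a matching lesion. SAP 5.5.3 nevertheless takes the maximum rCBV and the worst grade over lesions, so an unsampled lesion could be set against another lesion's histology.
- **BH formula.** SAP 3.8 omits the running minimum.

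**Working it through.** **The plan's own figure.** The documents size only the primary test. With 94% in both arms, margin 0.12, one-sided 2.5% and 80% power, n = (1.960 + 0.842)² × 2 × 0.94 × 0.06 / 0.12² = 61.5, so 62 per arm. Then 124 / 0.9 = 137.8, so 138. This reproduces. There is no figure for the rCBV comparison.

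**Assumptions.** The documents give no AUC, grade mix, histology count or BH family size. Assumed here: binormal rCBV with SD 1 and separation d = √2 × Φ⁻¹(AUC); 20 low and 42 high grade per arm (all 62 evaluable) or 10 and 15 (a histology subset); two-sided 5% Mann-Whitney tests; four tests per BH family. Results are by simulation.

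**Step 1: within-arm tests when the agents are equal.** Percentage of trials with exactly one arm significant:

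| True AUC, both arms | 20/42 unadjusted | 20/42 after BH | 10/15 unadjusted | 10/15 after BH |
|---|---|---|---|---|
| 0.70 | 38 | 38 | 47 | 26 |
| 0.75 | 15 | 22 | 48 | 35 |
| 0.80 | 3 | 5 | 36 | 36 |
| 0.85 | 0.1 | 0.3 | 16 | 23 |

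The BH columns correspond to the planned procedure, given four tests. BH can raise or lower the rate.

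**Step 2: within-arm tests when the agents differ.** With true AUCs of 0.75 and 0.90 at 20/42, both arms are significant (unadjusted) in about 92% of trials. A real gap of 0.15 would usually read as both agents discriminating.

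**Step 3: between-arm level tests at 20/42, unadjusted.** Percentage of trials with at least one of the two significant:

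- No AUC difference (0.80 in both), uniform shift of 0.25, 0.3 or 0.5 SD: about 28%, 37% or 72%.
- AUC 0.70 against 0.90: 78% if the gap is split over both grades, 90% if it lies in low grade only, over 99% if in high grade only.

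Among significant trials, the two grade-specific differences point the same way in 94% under the 0.5 SD shift and in about 5% under the split gap. If the gap lies in one grade only, they agree about half the time, so direction does not help.

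**Step 4: why a shift still matters at 1.75.** For AUC 0.80, d = 1.190. With the cut-off assumed midway, sensitivity and specificity are both Φ(0.595) = 72%. After a 0.5 SD shift they are Φ(1.095) = 86% and Φ(0.095) = 54%, with the AUC unchanged.

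**Step 5: precision of the missing estimate.** The Hanley-McNeil variance is [A(1−A) + (n₁−1)(Q₁−A²) + (n₀−1)(Q₂−A²)] / (n₁n₀), with Q₁ = A/(2−A) and Q₂ = 2A²/(1+A). For A = 0.80, n₁ = 42 and n₀ = 20, this is (0.160 + 1.093 + 1.351) / 840 = 0.00310, so SE = 0.0557. The half-width for a difference between two arms is 1.96 × √2 × 0.0557 = 0.154. At 10/15 it is 0.245. The simulated median DeLong half-widths are somewhat larger: 0.167 (AUC 0.80) to 0.185 (AUC 0.75) at 20/42, and 0.259 to 0.286 at 10/15. At 80%, Newcombe half-widths are 0.17 for sensitivity (42 per arm) and 0.25 for specificity (20 per arm), or 0.28 and 0.34 at 15 and 10 per arm.

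**Step 6: the BH formula.** Take p = 0.001, 0.026, 0.030, 0.034. SAP 3.8 multiplies by 4/j, giving 0.004, 0.052, 0.040, 0.034, so the second smallest p-value gets the largest adjusted value. With the running minimum the results are 0.004, 0.034, 0.034, 0.034. The literal formula changed a conclusion in at most about 3% of simulated trials, always in the conservative direction.

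**The case against.** The strongest reply is that the contrast is already there. Tables 14.2.2.23 to 14.2.2.26 give counts by arm, from which sensitivity, specificity and their differences follow. This stands. A reader might infer that the plan says nothing about how far apart the agents are; the documents do not support that. What is missing is a planned between-arm estimate with its precision.

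A reader might also infer that the level tests cannot tell a shift from a change in discrimination. That is too strong. The near-match of 72% and 78% depends on an assumed 0.5 SD shift; at 0.25 SD the rate is about 28%. The direction of the two grade-specific differences often separates the cases, though not when the gap lies in one grade.

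Unadjusted one-arm-only rates would overstate the problem in places (47% against 26% at 10/15, AUC 0.70), because BH adjustment is planned. Family size is itself uncertain, since results are shown per reader and overall.

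The Imaging Charter, which is not available here, may settle the overall value and the matching. Protocol 8.4 supports reading the overall value as unclear, but it is an ambiguity and not a proven error. SAP 2.2.2 places the rCBV analyses at patient level, and the number of patients with several lesions is unknown, so the matched-lesion point has no size attached.

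Finally, the added intervals will be wide. That is true, but it does not argue for leaving the precision unstated.

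**Conclusion.** The point holds. A comparative objective on differentiating grade has no planned between-arm estimate of discrimination with an interval. That follows from the text and table list and rests on no assumption; confidence is high.

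Confidence in the magnitudes is moderate, because they depend on the assumed binormal model, AUCs, grade mix, histology count and family size. Misleading one-arm-only results are plausible at moderate AUC or in a small histology subset, and all but vanish at AUC 0.85 with 20/42 per arm.

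The three definitions should be settled with it; the BH formula is the minor one. The primary non-inferiority conclusion is untouched. This should be corrected, but it does not put the trial's main result in doubt.

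**What to change.** Keep the planned tests and tables, and make these changes.

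1. **Add, as estimation only and outside the BH family:** the Elucirem minus Dotarem difference in ROC AUC of rCBV with a two-sided 95% interval (DeLong, independent samples), and the differences in sensitivity and specificity at 1.75 with 95% intervals (Newcombe). Use histopathology grade as the reference and stratification grade as support, since the latter may be only suspected. State that histology covers only patients with biopsy or surgery within 30 days. To limit the number of intervals, make the overall read on the Off-site PPS the main one, with the Off-site FAS and the single readers as support.
2. **Overall value:** reconcile SAP 5.5.3 with SAP 1.2 and Protocol 8.4, check the Imaging Charter, and state one rule. One option is the maximum of the two readers for every patient, with the consensus grade used only in the 1.75 tables.
3. **Histology analyses:** use the matched lesion's rCBV and rCBV-based grade instead of the maximum or worst over lesions.
4. **SAP 3.8:** take the running minimum from the largest p-value downwards.

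Cost: no new data and modest programming. Item 1 is purely an addition, but the other items are not. Item 2 may change the overall rCBV results, item 3 changes the input to Tables 14.2.2.19 to 14.2.2.22 and 14.2.2.25 to 14.2.2.26, and item 4 changes planned adjusted p-values. SAP version 4.0 is dated December 2024, and under Protocol 5.3.2 only the off-site readers are blinded. All four items therefore belong in SAP section 4 as dated late changes.

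The result will show the imprecision; it will not be a powered comparison. For AUC 0.70 against 0.90, a DeLong test would reject in about 69% of trials at 20/42 and 34% at 10/15.
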